## PURPOSE

To overcome the lack of knowledge regarding the physiological effects after hospital-based CR program, a 12 month RCT study will be performed. This study will hopefully contribute to generate evidence-based exercise prescription approaches to prolong the ET after the end of hospital-based CR programs.

The purpose of this research project is twofold:

1) To conduct a 12-month randomized control trial to evaluate the effects of periodized ET regime versus a non periodized ET regime on VO2 peak, maximal strength, body composition, functionality and quality of life in CVD patients.

2) to differentiate the effects of a 12-month periodized ET regime versus a non periodized ET regime on the different components of the oxygen kinetics response and oxidative adaptations in CVD patients.

The primary end points for aim 1 are: cardiopulmonary exercise testing (CPET) variables such as VO2 peak, AT, peak work rate, ventilatory equivalent of carbon dioxide (VE/VCO2), ventilatory equivalent of oxygen (VE/VO2), minute ventilation (VE), one repetition maximum (1RM), total body bone mineral content, lean and fat tissue mass and percentage of body fat mass, quality of life and functional physical fitness tests. The primary end points for aim 2 are oxygen kinetics and muscle deoxygenation dynamics of the vastus lateralis muscle at the submaximal test.

The hypothesis for this study are: 1) considering that this type of periodization exerts higher stress on the cardiovascular and neuromuscular systems, so that there could be greater adaptations, leading to higher increases in VO2max, muscle strength, body composition and functionality compared to non periodized ET regime; 2) there will be a better improvement microvascular O2 delivery in the exercise transient in response to periodized ET regime that would be associated with a faster adjustment of pulmonary VO2 kinetics than in non periodized group. Improvements in microvascular O2 delivery would be indicated by a better matching between the rate of adjustment of muscle deoxygenation relative to phase II pulmonary VO2, which represents a decreased reliance on O2 extraction for a given pulmonary VO2.

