## EXPECTED RESULTS

The variables measured in this task are primary endpoints of aim 1 of the project, it is expected improvements in the quality of life for both exercise training groups and a bi-directional relationship with increased physical activity and vocational status.

---

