### 13. STATISTICAL ANALYSIS

Data will be analyzed in M0, M1, M2 and M3. It will be tested the data for normality and homogeneity of variance with the Shapiro Wilk and Levene's tests, respectively. Data analysis will be described according to the established purposes for this project (descriptive values: mean, standard deviation, range, % change) and comparisons of means will be used for all purposed outcomes intra and inter groups. Baseline characteristics between groups will be evaluated with oneway ANOVA. Mixed between within subjects ANOVA will be conducted in a 2 (pre vs post ET) design to assess efficiency of the program. When a significant interaction is observed, t tests, or Wilcoxon signed-rank tests will be used to determine where the interaction occurred.

M0 versus M1, M0 versus M2, M0 versus M3, M1 versus M2, M2 versus M3 and M1 versus M3 will be compared to evaluate the changes in patients and trace the necessary timespan for such changes using General Linear Mixed Model Analysis for repeated measures with Tukey's posthoc procedure for the mean comparisons. Pearson product moment correlation coefficient or Spearman's rank correlation coefficient will be used to study the relationship between different variables by group and correlation coefficients will be compared between groups. Statistical significance will be set at an alpha level of 0.05. Other statistical procedures can be done.

Statistical analyses will be conducted using Statistical Package for the Social Sciences (SPSS) 22.0 (IBM SPSS Statistics, Chicago, IL, USA).

Data analysis will allow peer reviews redaction, slide presentations and oral communications in national and international conferences at the end of 2017 beginning of 2018.

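### Correlations among unlisted variables, and their comparison between arms, are tested at an unadjusted 0.05 with no exploratory label, so the false-positive risk is uncontrolled and depends on how many pairs are run (minor)

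*Combined protocol and SAP*

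**What the plan says.** Section 13 plans Pearson or Spearman coefficients that "will be used to study the relationship between different variables by group and correlation coefficients will be compared between groups". It does not say which variables or pairs are meant, whether levels or changes are correlated, at which visit, or by what test the arms' coefficients are compared.

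The significance rule is general: "Statistical significance will be set at an alpha level of 0.05". The only multiplicity procedure in the section is tied to another analysis, the visit-to-visit contrasts, "with Tukey's posthoc procedure for the mean comparisons". The section also states "Data will be analyzed in M0, M1, M2 and M3" and adds "Other statistical procedures can be done".

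Elsewhere the protocol mentions two associations. Hypothesis 2 in the Purpose section expects better microvascular oxygen delivery "that would be associated with a faster adjustment of pulmonary VO" kinetics. The expected results for the quality of life questionnaire (section 9) mention "a bi-directional relationship with increased physical activity and vocational status". Section 13 does not restrict the correlations to these, or separate them from any others.

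**The concern.** The number of possible pairs grows roughly with the square of the number of variables, and this protocol measures many. If each pair may be tested at 0.05 in each arm and again between arms, the plan sets no limit on how many chances there are for a significant result. A reader of the final report could not tell an association planned in advance from one picked out of many.

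At stake is what may be claimed. Under the stated rule, an unplanned association could be reported as a significant mechanism, and a chance gap between two coefficients as a significant difference in mechanism between periodized and non periodized training.

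**Working it through.** The plan gives no number of correlations and no error rate for them, so there is no stated figure to reproduce. The check asks what the 0.05 rule implies for different numbers of variables.

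**Inputs**
- Alpha 0.05 (section 13). Sidedness is not stated; two-sided is assumed.
- 25 patients per arm and 37% expected dropout (Participants section). Completers: 25 × (1 − 0.37) = 15.75, about 16 per arm.
- Variables: the aim 1 primary endpoints in the Purpose section, a list ending in "quality of life and functional physical fitness tests". They number 13 if 1RM, quality of life and the fitness tests each count once. The two aim 2 endpoints make 15.
- Assumption: the true correlation of each pair is the same in both arms, with a common r between 0 and 0.5.

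**Between-arm comparisons at one time point**

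For k variables there are m = k(k − 1)/2 pairs. The expected number of false differences is 0.05m. If the tests were independent, the chance of at least one would be 1 − 0.95^m. The pairs share variables, so this was also simulated with normal data. Each pair was compared by Fisher's z, counting a difference when |z₁ − z₂| / √(2/(n − 3)) > 1.96.

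| k | m | Expected false differences | 1 − 0.95^m | Simulated, common r 0 to 0.5 |
|---|---|---|---|---|
| 3 | 3 | 0.15 | 0.14 | 0.13 to 0.16 |
| 5 | 10 | 0.5 | 0.40 | 0.34 to 0.42 |
| 8 | 28 | 1.4 | 0.76 | 0.63 to 0.78 |
| 13 | 78 | 3.9 | 0.98 | 0.88 to 0.98 |
| 15 | 105 | 5.25 | 0.995 | 0.94 to 1.00 |

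Repeated runs moved the ends of these ranges by no more than about 0.02, and 16 and 25 per arm give nearly the same results. The lower ends belong to r = 0.5, so real correlation between the measures lowers the risk but does not remove it. If the comparison is made at M0, randomization makes equal correlations true by design, and any significant arm difference there is chance. If all four visits were used, expected counts would add: for 13 variables, 4 × 3.9 = 15.6.

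**Power of the same comparison**

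Take true correlations of 0.2 and 0.6. The Fisher z values are 0.203 and 0.693, a difference of 0.490. With n = 16 the standard error is √(2/13) = 0.392, the ratio is 1.25, and power is about 24%. With n = 25 the standard error is √(2/22) = 0.302, the ratio is 1.63, and power is about 37%.

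**Within-arm threshold**

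The critical value is |r| = t/√(n − 2 + t²), with t the 97.5% point on n − 2 degrees of freedom.
- n = 16: 2.145/√(14 + 4.60) = 0.497.
- n = 25: 2.069/√(23 + 4.28) = 0.396.

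A true correlation below the threshold can be significant only if it is overestimated. In simulation at n = 16 with true r of 0.3 to 0.5, about 99% of significant estimates were too large.

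**The case against.** The strongest reply is that the plan does not promise to correlate everything with everything. A reader might infer that spurious findings are almost certain. The documents do not support that, because they never say how many pairs will be run. With 3 variables the between-arm figure is about 0.14, and for a single pair it is 0.05. Near-certainty requires pairwise testing of all the listed endpoints, which the text does not state. This stands, and it is why the conclusion is conditional.

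A reader might also infer that most significant within-arm correlations would be chance findings. That is not supported either. Several listed endpoints are closely linked by construction, such as fat mass and percentage of body fat. If half of the pairs were truly null at n = 16, the false share of significant within-arm results would be about 20% when the other pairs have r = 0.3, 9% at 0.5 and 5% at 0.7. Overestimation is the sound criticism within arms. Uncontrolled false positives are the sound criticism between arms.

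Third, hypothesis 2 might be read as resting on a correlation and so needing a confirmatory one. Its text describes how closely muscle deoxygenation tracks phase II oxygen uptake, with a better result expected in the periodized arm. The aim 2 endpoints fall under the planned comparisons of means. A correlation pooled over arms would not test the between-arm part of the hypothesis. An onset version would also need a curve fit that is not specified: section 3 gives an HHb model for off-kinetics only.

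Finally, no correlation is a primary endpoint, and neither the randomized comparison nor the sample size depends on one. This also stands and sets the severity. None of these replies supplies a list of pairs, an exploratory label or an adjustment.

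**Conclusion.** The concern holds as a minor point. Section 13 allows unplanned associations and arm differences in association to be declared significant with no control of error. If true correlations are equal in both arms with a common r of 0 to 0.5, the chance of at least one false arm difference per time point runs from about 0.14 (3 variables) to 0.88 or more (13 to 15 variables, all pairs). Which figure applies cannot be determined from the documents. The figures assume normal data, a Fisher z comparison and two-sided tests. The within-arm thresholds of about 0.50 (n = 16) and 0.40 (n = 25) mean that significant estimates of modest correlations will be too large. The primary comparisons are not affected.

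**What to change.** Add to section 13 a statement to this effect: all within-arm correlations and all between-arm comparisons of correlation coefficients are exploratory, and are reported as estimates with 95% confidence intervals and without claims of significance.

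The alternative is to control the false discovery rate over the full list tested. That list, the time point and the comparison test would then have to be written down before analysis.

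Leave hypothesis 2 with the planned between-arm comparison of the aim 2 endpoints, and add no new confirmatory correlation.

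The cost is a few sentences, with no new data, visits or patients. The downside is that correlation results can no longer be reported as significant at an unadjusted 0.05. The descriptive information is kept.
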